1.0 STUDY SCHEMA

[figure not shown]
1.1 BiRd medication schedule (one cycle)

Lenalidomide will be given for days 1-21 followed by a 7 day rest period for each 28-day cycle.

*Dexamethasone at a dose of 20mg on Days 1, 8, 15, 22 will be used for subjects ≤ 75 years old.

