3.8 Rationale for BiRD Combination in Multiple Myeloma

While new anti-myeloma therapies such as bortezomib and immunomodulatory drugs have been developed, multiple myeloma remains an incurable malignancy. Given that obtaining a complete remission with therapy will allow patients with newly diagnosed multiple myeloma to enjoy a higher quality of life and longer duration of freedom from disease symptoms, finding an optimally effective and well-tolerated regimen is imperative.

Based on the immunodulatory effect of biaxin, the unique anti-myeloma activity of lenalidomide, and the synergistic properties of dexamethasone, the combination of BiRd has demonstrated to be highly effective in the treatment of multiple myeloma, and is anticipated to provide superior outcomes when compared to lenalidomide and dexamethasone therapy alone. A phase II study of clarithromycin (500mg twice daily), lenalidomide (25mg daily for 21 days out of a 28 day cycle), and low dose dexamethasone (40mg weekly) called the BiRd regimen was conducted.³⁰ By replacing thalidomide with lenalidomide into our former BLTD treatment platform, we achieved an overall response rate of 90.3%, and a higher CR rate compared with the earlier BLTD data, 30% vs. 13%. Retrospective case matched analysis comparing patients induced with BiRd vs Rd found that the addition of clarithromycin to Rd significantly increased patient's rate of response, with 90.3% vs 79.1% of patients achieving PR or greater, and 45.8% vs 13.9% of patients achieving CR.³¹ While promising, randomized phase III studies are needed to confirm the superiority of BiRd compared with RD in terms of response rates and survival.

This study is intended to investigate the efficacy of combination therapy with an induction phase utilizing a combination clarithromycin (Biaxin[®]), lenalidomide (Revlimid[®]), dexamethasone (Decadron[®]), in multiple myeloma patients who are newly diagnosed and require treatment when compared to patients who receive lenalidomide

and dexamethasone alone. Randomized phase III studies are needed to confirm the superiority of BiRd compared with Rd in terms of response rates and survival. We anticipate the addition of lenalidomide and bixin will lead to a greater CR rate, shorter times to response, and less toxicity. The primary endpoints of this trial include best response rate, toxicities, progression free survival, event free survival, and overall survival.

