4.0 INVESTIGATIONAL PLAN

4.1 Study Design

This phase III study, open-label, randomized study investigating lenalidomide and dexamethasone with and without bixin in subjects with newly diagnosed, previously untreated multiple myeloma. Eligible subjects will be randomized in a 1:1 ratio to receive a regimen consisting of either bixin, lenalidomide, and low dose dexamethasone (BiRd arm), or lenalidomide and low dose dexamethasone (Rd arm). Up to 306 patients will be enrolled.

BiRd Arm

Subjects on the BiRd arm will receive bixin, revlimid, and dexamethasone in 28-day cycles. Dosing is as follows:

- Clarithromycin 500mg PO twice daily on days 1-28 for a 28-day cycle. If a dose of clarithromycin is missed, it should be taken as soon as possible on the same day. If it is missed for the entire day, it should not be made up. Vomited doses will not be made up.
- Lenalidomide 25mg PO daily on days 1-21 of a 28-day cycle for patients with a calculated creatinine clearance of ≥ 60 cc/min. Patients with a calculated creatinine clearance of < 60 cc/min will receive 15 mgs PO daily on days 1-21 of a 28 cycle. If a dose of lenalidomide is missed, it should be taken as soon as possible on the same day. If it is missed for the entire day, it should not be made up. Vomited doses will not be made up.
- Dexamethasone 40mg PO will be given on days 1, 8, 15, 22 of a 28-day cycle. Missed or vomited doses will not be made up. If subject cannot tolerate oral dexamethasone, it will be given intravenously.

Rd Arm

Subjects on the Rd arm will receive revlimid, and dexamethasone in 28-day cycles. Dosing is as follows:

- Lenalidomide 25mg PO daily on days 1-21 of a 28-day cycle for patients with a calculated creatinine clearance of ≥ 60 cc/min. Patients with a calculated clearance of < 60 cc/min will receive 15 mgs PO daily on days 1-21 of a 28 cycle. If a dose of lenalidomide is missed, it should be taken as soon as possible on the same day. If it

is missed for the entire day, it should not be made up. Vomited doses will not be made up.

- Dexamethasone 40mg PO will be given on days 1, 8, 15, 22 of a 28-day cycle. Missed or vomited doses will not be made up. If subject cannot tolerate oral dexamethasone, it will be given intravenously.

Correlative studies: Relative dose intensity: Projected total dose per cycle of each component of assigned drug will be divided by the actual dose received and a ratio will be assessed for each cycle delivered.

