5.0 CRITERIA FOR PATIENT ELIGIBILITY

5.1 Inclusion Criteria

Each subject must meet all of the following inclusion criteria to be eligible to participate in this study:

- Subject must voluntarily sign and understand written informed consent.
- Subject is ≥ 65 years at the time of signing the consent form.
- Subject has histologically confirmed multiple myeloma that has never before been treated (see Appendix II).
- Subject has no prior anti-myeloma treatment therapy within 14 days prior to initiation of study treatment except for corticosteroids with a maximum allowed dosage equivalent to three pulses of dexamethasone (40mg daily for 4 days equals one pulse). Patients may have received prior adjuvant antiresorptive therapy (i.e., pamidronate or zoledronic acid) as routine care, or radiation therapy as palliation for pain and/or spinal cord compression.
- Subject has measurable disease as defined by > 0.5 g/dL serum monoclonal protein, > 10 mg/dL involved serum free light chain (either kappa or lambda) provided that the serum free light chain ratio is abnormal, > 0.2 g/24 hrs urinary M-protein excretion, and/or measurable plasmacytoma(s) of at least 1cm in greatest dimension as measured by either CT scanning or MRI.
- Subject has a Karnofsky performance status $\geq 60\%$ ($> 50\%$ if due to bony involvement of myeloma (see Appendix IV).
- Subject is able to take prophylactic anticoagulation as detailed in section 9.1 (patients intolerant to aspirin may use warfarin or low molecular weight heparin).
- Subject is registered into the mandatory RevAssist® program, and is willing and able to comply with the requirements of RevAssist® program.
- If subject is a female of childbearing potential (FCBP),† she must have a negative serum or urine pregnancy test with a sensitivity of at least 25 mIU/mL within 10 – 14 days prior to and again within 24 hours of prescribing lenalidomide (prescriptions must be filled within 7 days) and must either commit to continued abstinence from heterosexual intercourse or begin TWO acceptable methods of birth control, one highly effective method and one additional effective method AT THE SAME TIME, at least 28 days before she starts taking lenalidomide. FCBP must also agree to ongoing pregnancy testing. Men must agree to use a latex condom during sexual contact with females of child bearing potential even if they have had a successful vasectomy. See

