9.0 Therapeutic Plan

9.1 Treatment

Patients who sign informed consent will be seen in clinic or in the hospital at New York Presbyterian Hospital-Weill Cornell Medical College, by their physician for pretreatment testing as outlined in section 6.0. All prescribers must be registered in the Celgene RevAssist® program in order to prescribe lenalidomide (Revlimid®). Subjects who complete pretreatment evaluations and meet all eligibility criteria may start treatment. All patients will be started on BiRd in 28-day cycles according to the following schedule:

For all subjects, **Dexamethasone** (Decadron®) will be given orally at a dose of 40 mg on days 1, 8, 15, and 22 for each subsequent cycle

For subjects on the BiRd arm only, **Clarithromycin** (Biaxin®) will be given orally at a dose of 500 mg twice a day, beginning on day 1 of cycle 1.

For all subjects, **Lenalidomide** (Revlimid®) will be given orally at a dose of 25 mg/day beginning on day 3 and ending on day 21 of cycle 1, and on days 1-21 of each subsequent cycle.

Due to the risk of thrombosis (see Section 8.5), all patients will begin thromboembolic prophylaxis with aspirin 81mg daily throughout treatment, starting on cycle 1 day 1. Aspirin-intolerant patients, or patients with a prior history of venous thrombosis, should receive prophylactic doses of daily low molecular weight heparin (LMWH). For patients who are unable to take aspirin or LMWH, other antithrombotic agents may be used at the investigators discretion. If warfarin is used, the INR should be monitored frequently to maintain within the goal range of 2-3. Concurrent use of recombinant erythropoietin to treat anemia is discouraged due to reports of increased thromboembolic events in patients receiving lenalidomide with erythropoietin. Concurrent use of erythropoietin requires full anticoagulation of patients with

therapeutic doses of LMWH or coumadin. Anticoagulation should be held for platelet counts <50,000/mm³.

Monitoring for Secondary Primary Malignancies

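### The BiRd example diary halves the clarithromycin dose as written; the dexamethasone age note probably has its inequality reversed and appears in no other dosing section

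*Combined protocol and SAP*

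**What the plan says.** **Clarithromycin.** Section 4.1 gives the BiRd arm "Clarithromycin 500mg PO twice daily on days 1-28 for a 28-day cycle". Section 9.1 agrees: the drug "will be given orally at a dose of 500 mg twice a day, beginning on day 1 of cycle 1". Table 1 in section 9.6 has the same starting dose, and section 3.8 describes the earlier phase II regimen as 500 mg twice daily. The instruction line of the BiRd example diary (Appendix VIII) differs: it tells the patient to take one 500 mg pill per day. The calendar below that line prints two boxes for Biaxin on each day it is listed.

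**Dexamethasone.** The notes to the BiRd and Rd medication schedules (both numbered 1.1) read identically: "Dexamethasone at a dose of 20mg on Days 1, 8, 15, 22 will be used for subjects ≤ 75 years old". Section 5.1 requires that "Subject is ≥ 65 years at the time of signing the consent form". Section 4.1 states, for each arm, "Dexamethasone 40mg PO will be given on days 1, 8, 15, 22 of a 28-day cycle". Section 9.1 says that dexamethasone "will be given orally at a dose of 40 mg on days 1, 8, 15, and 22 for each subsequent cycle", and opens that line by applying it to all subjects. Table 1 starts at 40 mg, and both example diaries call for ten 4 mg pills once weekly. None of these four places mentions age.

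**Where the doses are used.** Section 10.1 has the drug diary generated and reviewed with the patient on Day 1 of Cycle 1 and refers to Appendix VIII for it. Relative dose intensity is objective 2.1.6, and section 4.1 defines it from the planned dose: "Projected total dose per cycle of each component of assigned drug will be divided by the actual dose received".

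**The concern.** Clarithromycin is the only drug that differs between the arms. A patient who follows the diary sentence takes half the intended dose of the agent under test, and this can happen only in the BiRd arm. The Appendix VIII diary is the one that section 10.1 points staff to, so the sentence could plausibly reach patients.

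The dexamethasone note raises a different question. An age rule that gives the lower steroid dose to the younger part of a population aged 65 and over, and the full dose to the oldest, runs opposite to what one would expect. If an age exception was intended, it is missing from every section and diary that staff and patients would use to set the dose. If none was intended, the note should not be there. Until this is settled, a site could start the same patient on 20 mg or 40 mg, and the projected dose for relative dose intensity depends on which is used.

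**Working it through.** The check compares the dosing statements and does simple arithmetic per 28-day cycle.

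**Clarithromycin** (planned dose from sections 4.1, 9.1 and Table 1; diary dose from Appendix VIII)
- Planned: 2 × 500 = 1,000 mg a day; 2 × 28 = 56 tablets, or 28,000 mg, per cycle.
- Diary sentence: 1 × 500 = 500 mg a day; 1 × 28 = 28 tablets, or 14,000 mg, per cycle.
- Ratio: 14,000 / 28,000 = 0.5. Shortfall: 56 − 28 = 28 tablets, or 14,000 mg, per cycle.
- Dose Level −1 in Table 1 is 250 mg twice daily: 2 × 250 = 500 mg a day. The diary sentence therefore gives the same daily total as a first dose reduction.

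**When the shortfall would be seen.** Section 10.0 has patients seen weekly in Cycle 1. Section 10.5 has staff review dosing instructions and count used and unused study drug at each visit.
- By the Day 8 visit, 7 days have passed: planned 7 × 2 = 14 tablets, taken 7 × 1 = 7, missed 7 tablets, or 7 × 500 = 3,500 mg.
- If the prescription, the dosing review and the counts all fail, the next scheduled check is collection of the completed diary on Day 1 of Cycle 2 (section 1.3). By then the shortfall is the full 28 tablets (14,000 mg).

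**Dexamethasone** (four doses per cycle)
- Under the note: 4 × 20 = 80 mg. Elsewhere: 4 × 40 = 160 mg. Ratio 160 / 80 = 2.
- With entry at 65 or over, the note as printed assigns 20 mg to ages 65 to 75 and leaves 40 mg for those over 75.
- Diary pills: 40 / 4 = 10, as printed; a 20 mg dose would need 20 / 4 = 5.
- Table 1 lists 20 mg as Dose Level −1 and 8 mg as Dose Level −2, so a subject who starts at 20 mg would go to 8 mg at the first reduction.
- Relative dose intensity for a subject who takes 80 mg in a cycle, as section 4.1 forms the ratio: 160 / 80 = 2 if the projected dose is taken as 40 mg weekly, and 80 / 80 = 1 if 20 mg weekly. Formed the other way round, the values are 0.5 and 1. The factor is 2 either way.

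The 20 mg weekly dexamethasone in section 9.1 does not explain the note. It belongs to maintenance and is triggered by response or plateau, not age.

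**The case against.** **On clarithromycin**, the intended dose is not in doubt, the appendix is headed as an example, and the drug is supplied on the investigator's prescription (section 7.1). With the visit-level checks in section 10.5, a misprint should be caught quickly. Most of this stands, and it limits the likely effect. It does not make the sentence correct. The protection from counts is also conditional: section 10.5 speaks of capsules in one sentence and of any unused study drug in the one before, and clarithromycin comes as tablets from the patient's local pharmacy. Whether the counts cover it is an assumption.

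**On dexamethasone**, a reader might infer that section 9.1 flatly contradicts the note because its 40 mg line covers all subjects. The documents do not support that. Section 9.1 sets the phrase against a line for the BiRd arm only, so it can mean both arms. It uses the same phrase for lenalidomide 25 mg, although section 4.1 gives 15 mg when creatinine clearance is below 60 cc/min. The phrase thus already coexists with an exception stated elsewhere, and the note can be read as a footnoted exception to a 40 mg default. It follows that the starting dose is not strictly undefined: read literally, it is 20 mg up to age 75 and 40 mg above.

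The inequality itself could also be a misreading of the PDF. Appendix I prints a reduction of at most 90% for very good partial response, beside at least 50% for partial response, so these signs are not reliable throughout the text. Against that, the same sign appears in both schedule notes. The schedule that carries the asterisk is not visible. These points lower confidence in the dexamethasone item, but they do not explain why no other dosing section or diary carries the age rule.

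**Conclusion.** The clarithromycin sentence is wrong as written. It halves the daily dose in the experimental arm only. The likely loss for a patient who follows it is about 7 tablets (3,500 mg) before the Day 8 visit, assuming the counts include clarithromycin. A reader might take 28 tablets (14,000 mg) as the expected loss before detection; that figure holds only if the prescription, the dosing review and the counts all miss the error. How many patients would be affected cannot be derived from the documents.

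The dexamethasone item holds with lower confidence. The direction of the age rule is probably inverted, and the rule appears only in the two schedule notes. Dexamethasone is 80 or 160 mg per cycle depending on the rule followed. The same note and the same 40 mg statements apply to both arms, so the documents give no ground for inferring a bias of BiRd against Rd from it. Its statistical effect is confined to relative dose intensity, which is not among the analyses in section 14.

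Sample size, required PFS events and power are unaffected.

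**What to change.** 1. In the BiRd diary (Appendix VIII), change the clarithromycin instruction to one 500 mg pill twice a day.
2. Decide whether an age-based dexamethasone dose is intended. If not, delete the note from both schedules. If so, correct its direction, carry the exception into sections 4.1 and 9.1, provide diary wording for five 4 mg pills in both arms, and state that the first reduction from 20 mg is to 8 mg (the existing Dose Level −2).
3. Use the reconciled starting dose as the projected dose for relative dose intensity.

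The cost is protocol wording and a reprinted diary. No extra patients, procedures or events are needed.

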1.1 Rd medication schedule (one cycle)

Lenalidomide will be given for days 1-21 followed by a 7 day rest period for each 28-day cycle.

*Dexamethasone at a dose of 20mg on Days 1, 8, 15, 22 will be used for subjects ≤ 75 years old.

1.3 Schedule of Assessments

Procedure	Screening <28 days prior to start date (unless otherwise indicated)	Cycle 1 Day 1	Cycle 1 Days 8, 15, 22	All Other Cycles Day 1	End of Study ⁹	Follow- Up Phase (Every 6 months)
Complete medical history with quality of life assessment.	X	X		X		
Physical exam, KPS, vital signs, height and weight	X	X		X		
CBC with differential	X	X	X	X	X	
Complete metabolic profile ^{1,2}	X	X	X	X ²	X	
Generate / review new drug diary		X		X		
Collect / review prior drug diary				X	X	
SPEP, IF, quantitative immunoglobulins ³	X	X		X	X	
Serum free light chains ³	X	X		X	X	
24-hour urine for UTP, UPEP, UIF ³	X	X		X	X	
β ₂ M ³	X					
CRP	X					
Urinalysis	X					
Pregnancy test ⁴	X	X		X	X	
Register patient into RevAssist [®] program ⁵	X					
Skeletal survey, MRI, or whole body PET/CT scan	X ⁶			X ⁸	X ⁸	
Bone marrow biopsy and aspirate ⁷	X ⁶			X ⁸	X ⁸	
Concurrent medication use survey	X	X		X		
Electrocardiogram	X					
Drug dispensation ⁶				Continuous		
Adverse event				Continuous		

monitoring						
Obtain Follow-Up anti-cancer treatments						X
Obtain disease status, physical status, survival information, and if any occurrence of secondary primary malignancies						X

1. Includes sodium, potassium, chloride, CO₂, calcium, blood urea nitrogen (BUN), serum creatinine and calculated creatinine clearance, glucose, albumin, total protein, alkaline phosphatase, total bilirubin, SGOT/AST, SGPT/ALT, LDH, Uric Acid. Phosphorus and magnesium are performed at screening and Cycle 1 Day 1.
2. To include Thyroid Stimulating Hormone (TSH) at screening, and every 3 months beginning with cycle 4 (more often if clinically indicated).
3. UTP = urine total protein; UPEP = urine protein electrophoresis; UIF = urine immunofixation; SPEP = serum protein electrophoresis; IF = serum immunofixation; β₂M = beta-2 microglobulin.
4. Pregnancy test for females of child-bearing potential (FCBP). A female of childbearing potential is a sexually mature woman who: 1) has not undergone a hysterectomy or bilateral oophorectomy; or 2) has not been naturally postmenopausal (amenorrhea following cancer therapy does not rule out childbearing potential) for at least 24 consecutive months (i.e., has had menses at any time in the preceding 24 consecutive months). Pregnancy tests must occur within 10 – 14 days and again within 24 hours prior to prescribing lenalidomide (prescriptions must be filled within 7 days). FCBP with regular or no menstruation must have a pregnancy test weekly for the first 28 days and then every 28 days while on therapy (including breaks in therapy), at discontinuation of lenalidomide (whichever comes later) and at Day 28 post the last dose of lenalidomide (whichever comes later). FCBP with irregular menstruation must have a pregnancy test weekly for the first 28 days and then every 14 days while on therapy (including breaks in therapy), at discontinuation of lenalidomide (whichever comes later) and at Day 14 and Day 28 post the last dose of lenalidomide (whichever comes later) (see Appendix III: Risks of Fetal Exposure, Pregnancy Testing Guidelines and Acceptable Birth Control Methods).
5. Lenalidomide must be prescribed through and in compliance with Celgene's RevAssist® program. Prescriptions of lenalidomide must be filled within 7 days.
6. To occur within 6 weeks of treatment
7. Iliac crest bone marrow aspirate for cytological review, including cytogenetics, FISH studies, flow cytometry (when available), and core biopsy for immunohistochemistry.
8. To confirm complete remission, progression, or when clinically indicated
9. An additional safety assessment will be done 30 days (+/- 7 days) following the last dose of study drug.

2.0 OBJECTIVES AND SCIENTIFIC AIMS

2.1 Study Objectives

- 2.1.1 To evaluate the efficacy of clarithromycin (Biaxin), lenalidomide (Revlimid), and dexamethasone (Decadron) combination therapy (BiRd), compared to lenalidomide and dexamethasone (Rd) alone as an induction therapy for patients with newly diagnosed, transplant ineligible, previously untreated multiple myeloma (MM).
- 2.1.2 To determine the progression free survival (PFS) of the BiRd regimen compared to Rd.
- 2.1.3 To compare objective response rate (ORR) of BiRd versus Rd.
- 2.1.4 To determine and compare duration of response (DOR), event free survival (EFS), time to progression (TTP), and overall survival (OS) of BiRd versus Rd.
- 2.1.5 To assess safety and drug toxicity in each arm.
- 2.1.6 To determine relative dose intensity for each component of protocol medication prescribed.
- 2.1.7 To evaluate and compare minimal residual disease following therapy of BiRd versus Rd.
- 2.1.8 To determine and compare the PFS2 (time from study entry until 2nd instance of disease progression) of BiRd versus Rd.
- 2.1.9 To assess determine and compare quality of life assessments for BiRd vs Rd.

2.2 Study Endpoints

- Progression free survival
- Response rate by IMWG criteria (see Appendix I)
- Event free survival (an event is defined by coming off protocol for any reason, including progression of disease, lack of disease response, regimen intolerance, or death).
- Overall survival
- Duration of response
- Time to progression
- Progression free survival 2: time from study entry until 2nd instance of disease progression

- Quality of life: as measured by Functional Assessment of Chronic Illness Therapy – Fatigue (FACIT-Fatigue) Scale (Appendix IX) as part of a quality of life assessment.
- Regimen toxicities, as defined by CTCAE V4.0

3.0 BACKGROUND AND RATIONALE

3.1 Disease Information

Multiple Myeloma (MM) is a neoplastic disorder of unknown etiology characterized by an abnormal proliferation of plasma cells producing excess quantities of a single immunoglobulin protein isotype (M-protein). Malignant plasma cells expand and accumulate in the bone marrow, leading to cytopenias, imbalance of bone formation and resorption, and the production of monoclonal protein.¹ It is estimated that over 21,000 new cases of myeloma are diagnosed in the US each year accounting for approximately 1% of all cancers and 10-15% of all hematological malignancies.² The disease is twice as common in persons of African descent as compared to Caucasians. MM usually occurs in older individuals with a median age of 69 years old.³ There is currently no cure, and available therapies are only able to slow disease progression, prolong survival, and minimize symptoms.

